4.2 Exclusion Criteria

At each registration, patients meeting any of the following criteria will be ineligible. The rationale is shown in Section [14.3](#).

4.2.1 Registration in the Observation Period

- (1) Having the following concurrent or historical conditions, and having been diagnosed with neurogenic bladder accompanied by obvious neurological abnormality associated with the following diseases
 - 1) Cerebrovascular disorder (cerebral hemorrhage, cerebral infarction, etc.)
 - 2) Parkinson's disease
 - 3) Alzheimer's disease
 - 4) Multiple sclerosis
 - 5) Spina bifida
 - 6) Spinal cord disorder (spinal cord injury, etc.)
- (2) Concurrent urinary tract infection (prostatitis, cystitis, etc.) or historical recurrent urinary tract infection [occurring ≥ 3 times within a period of 168 days (24 weeks) before registration in the observation period]. Concurrent urinary disease impairing determination of the effect of the investigational drug, such as cystitis interstitial, urinary tract stenosis, urinary tract obstruction, calculus urinary (calculus ureteric, calculus urethral, calculus bladder, etc.), benign tumor of the urethra (urethral polyp, cyst, papilloma, etc.) and urethral diverticulum.
- (3) Concurrent bladder cancer or prostate cancer, or suspected bladder cancer or prostate cancer, or a history of these
- (4) Cystocele classified as stage III or higher according to the POP-Q stage classification (females)
- (5) Prostate gland volume ≥ 30 mL (males)
- (6) Overflow urinary incontinence

- (7) Clinically significant concurrent conditions (including symptoms and findings) such as severe liver disease (hepatitis viral, drug-induced liver injury, etc.), severe renal disease (acute renal failure, glomerulonephritis, nephritis interstitial, etc.), severe cardiovascular disease (cardiac failure congestive, symptomatic unstable angina pectoris, poorly controlled arrhythmia, myocardial infarction, etc.), severe blood dyscrasia (pancytopenia, leukopenia, etc.), severe respiratory disease (bronchial asthma, bronchitis chronic, etc.), severe digestive disease (peptic ulcer, reflux esophagitis, Crohn's disease, colitis ulcerative, etc.), severe neuropsychiatric disease (schizophrenia, dementia, etc.), severe immune disease (collagen disorder, etc.), severe metabolic or endocrine disease or malignant tumor
- (8) Having received urethral catheter placement, or performing intermittent self-catheterization due to the inability to urinate spontaneously
- (9) Meeting the following conditions at laboratory tests performed in the period of 14 days before registration in the observation period
 - 1) Aspartate aminotransferase (AST) $> 3 \times$ upper limit of normal (ULN)
 - 2) ALT $> 3 \times$ ULN
 - 3) T-Bil $> 1.5 \times$ ULN
 - 4) Serum creatinine $> 1.5 \times$ ULN
- (10) The following have been performed in the period of 154 days (22 weeks) before registration in the observation period.
 - 1) Surgery of the pelvic organs (radical hysterectomy, radical surgery for rectal cancer, radical pelvic lymph node dissection, etc.) injuring the pelvic nerve or hypogastric nerve
 - 2) Prostatectomy
 - 3) Radiotherapy that may affect voiding function
- (11) Having received another investigational drug in the period of 90 days before registration in the observation period
- (12) Being pregnant, breastfeeding, or a female patient of childbearing potential with a positive (urine or serum) pregnancy test result in the period of 7 days before registration in the observation period
 - Note) Women without childbearing potential are women who have undergone hysterectomy and postmenopausal women who have not experienced menstruation for at least 1 year with no associated medical reason such as administration of contraceptives
- (13) In the case of women with reproductive potential, not consenting to use contraception during the study period and for a period of 30 days after the end of administration of the investigational drug*
- (14) In the case of male patients, not consenting to use contraception during the study period and for a period of 90 days after the end of administration of the investigational drug*

(15) Being determined to be ineligible for this study in the opinion of the principal investigator or subinvestigator

* The principal investigator or subinvestigator will instruct patients to always perform contraception using a method such as the double-barrier method (a condom and pessary), an intrauterine device or oral contraceptives during the period of administration of the investigational drug and the period of contraception after the end of administration of the investigational drug.

4.2.2 Registration in the Treatment Period

- (1) A rate of compliance with administration of the investigational drug of <80% in the observation period
- (2) Having the following concurrent conditions, and having been diagnosed with neurogenic bladder accompanied by obvious neurological abnormality associated with the following diseases
 - 1) Cerebrovascular disorder (cerebral hemorrhage, cerebral infarction, etc.)
 - 2) Parkinson's disease
 - 3) Alzheimer's disease
 - 4) Multiple sclerosis
 - 5) Spina bifida
 - 6) Spinal cord disorder (spinal cord injury, etc.)
- (3) Concurrent urinary disease impairing determination of the effect of the investigational drug, such as urinary tract infection (prostatitis, cystitis, etc.), cystitis interstitial, urinary tract stenosis, urinary tract obstruction, calculus urinary (calculus ureteric, calculus urethral, calculus bladder, etc.), benign tumor of the urethra (urethral polyp, cyst, papilloma, etc.) and urethral diverticulum.
- (4) Concurrent bladder cancer or prostate cancer, or suspected bladder cancer or prostate cancer
- (5) Cystocele classified as stage III or higher according to the POP-Q stage classification (females)
- (6) Overflow urinary incontinence
- (7) Clinically significant concurrent conditions (including symptoms and findings) such as severe liver disease (hepatitis viral, drug-induced liver injury, etc.), severe renal disease (acute renal failure, glomerulonephritis, nephritis interstitial, etc.), severe cardiovascular disease (cardiac failure congestive, symptomatic unstable angina pectoris, poorly controlled arrhythmia, myocardial infarction, etc.), severe blood dyscrasia (pancytopenia, leukopenia, etc.), severe respiratory disease (bronchial asthma, bronchitis chronic, etc.), severe digestive disease (peptic ulcer, reflux esophagitis, Crohn's disease, colitis ulcerative, etc.), severe neuropsychiatric disease (schizophrenia, dementia, etc.), severe immune disease (collagen disorder, etc.), severe metabolic or endocrine disease or malignant tumor

- (8) Having received urethral catheter placement, or performing intermittent self-catheterization due to the inability to urinate spontaneously
- (9) Being determined to be ineligible for this study in the opinion of the principal investigator or subinvestigator

4.3 Discontinuation Criteria for Individual Patients

Administration of the investigational drug will be discontinued in a patient meeting any of the following criteria. Discontinuation criteria for individual patients are shown below:

- (1) It becomes unfeasible to continue administration due to the occurrence of an adverse event
- (2) The patient requests withdrawal of his/her consent
- (3) Major noncompliance with the study procedures is observed.
- (4) The patient becomes unable to continue the study due to circumstances such as moving house, being transferred to another medical institution or being too busy
- (5) It is discovered that the patient is not in the target population for this study (the patient does not meet the inclusion criteria, or meets any of the exclusion criteria).
- (6) The patient becomes pregnant.
- (7) Because the effect of the investigational drug is incomplete or symptoms have worsened, the principal investigator or subinvestigator determines that administration should be discontinued.
- (8) It becomes necessary to discontinue the patient from the study for any other reason in the opinion of the principal investigator or subinvestigator.

5. STUDY ASSESSMENTS

The evaluations and examination items to be performed in this study are shown in [Table 5-1](#) and the detailed schedule is shown in [Table 5-2](#).

All information stipulated in the protocol should be recorded. If the designated observations or tests are performed in the period of 14 days before registration in the observation period, even if this is before informed consent is obtained, these can be used as data at registration in the observation period.

Table 5-1 Evaluations and Examination Items

Obtaining informed consent					
Date of obtaining informed consent					
Patient backgrounds					
Sex	Date of birth	Age ^{*1}			
Race	Height	Weight			
BMI ^{*2}	History of participation in clinical studies (within the past 90 days)	Medical history (within the past 180 days) ^{*3}			
Onset time of lower urinary tract symptoms (LUTS) (storage symptoms, voiding symptoms, and post-micturition symptoms)					
Concurrent conditions	History of prior treatment				
Patient registration					
Patient identification code	Drug number				
Symptoms and findings					
Blood pressure (systolic and diastolic)	Pulse rate	Body temperature			
Compliance with administration of the investigational drug					
Concomitant medication and concomitant therapy					
12-lead electrocardiography					
Heart rate	QT interval	RR interval	QTcF interval ^{*4}		
Hematology tests					
Red blood cell count	Hemoglobin	Hematocrit	Platelet count		
White blood cell count	Neutrophils	Eosinophils	Basophils		
Lymphocytes	Monocytes				
Biochemistry tests					
Total protein	Albumin	A/G	T-Bil		
Direct bilirubin	AST(GOT)	ALT(GPT)	ALP		
LDH	γ-GTP	BUN	Creatinine		
Creatine kinase	Blood glucose	Amylase	Triglycerides		
Total cholesterol	CRP	Na	K		
Cl	Ca ^{*5}				
Endocrinological tests					
Thyroid stimulating hormone (TSH)	free T ₃	free T ₄	Cortisol		
Adrenocorticotrophic hormone (ACTH)					
Urinalysis					
Protein	Glucose	Urobilinogen	Urine NAG		
Urine β ₂ -microglobulin	Urine sediment ^{*6}				
Pregnancy test ^{*7}					
Serum or urine human chorionic gonadotropin					
Prostate gland volume measurement					
Pressure flow study (PFS) (filling phase)					
Volume at first desire to void	Maximum bladder volume	Bladder compliance	Appearance of bladder involuntary contraction		
Bladder volume up to appearance of bladder involuntary contraction					
Pressure flow study (PFS) (voiding phase)					
BCI (P _{det} Q _{max} + 5Q _{max}): males		PIP1 (P _{det} Q _{max} + Q _{max}): females			
Detrusor pressure at maximum flow (P _{det} Q _{max})		Detrusor pressure at start of voiding (P _{det open})			
Maximum detrusor pressure (P _{det max})		Maximum flow rate (Q _{max})			
Average flow rate (Q _{ave})		Duration of bladder contraction			
Voided volume		Post void residual			
Uroflowmetry					
Maximum flow rate (free Q _{max})	Average flow rate (free Q _{ave})	Voided volume	Voiding time		
Post void residual measured by ultrasound					
be [voided volume/(voided volume + post void residual)]					
Post void residual measured by ultrasound and voided volume measured by uroflowmetry					
Symptom score evaluation					
IPSS	OABSS				
QOL score evaluation					
KHQ					
Bladder diary records					
Dates and times of voiding and urinary incontinence	Urinary urgency	Voided volume			
Evaluation of adverse events					

*1: Automatically calculated from the date of birth. *2: Automatically calculated from height and weight.

*3: This is a medical history determined by the principal investigator or subinvestigator to be important in the conduct of this study (such as diseases related to urinary organs).

*4: Automatically calculated from the QT interval and RR interval.

*5: In the evaluation of adverse events, if albumin is < 4.0 g/dL, determinations will be made using values corrected by the following formula.

$$[\text{Corrected calcium (mg/dL)}] = [\text{Calcium (mg/dL)}] - 0.8 \times \{[\text{Albumin (g/dL)}] - 4\}$$

*6: Urine sediment will only be examined at registration in the observation period and registration in the treatment period.

*7: Required for female patients with childbearing potential. However, a pregnancy test will not be required for patients more than 1 year after menopause or patients in whom the possibility of pregnancy is medically ruled out.

Table 5-2 Observation and Testing Schedule

Timing	Observation period		Treatment period							Follow-up period	At discontinuation ⁸⁾	
	At registration	3 days before registration in the treatment period	At registration ⁵⁾	Week 2 ⁶⁾	3 days before the visit for week 4	Week 4 ⁶⁾	3 days before the visit for week 8	Week 8 ⁶⁾	3 days before the visit for week 12	Week 12 ⁶⁾		
Visit	1		2	3		4		5		6	7	
Week	-4 to -2		0	2		4		8		12	13	
Obtaining informed consent	X ¹⁾											
Assigning of patient identification codes ²⁾	X											
Patient backgrounds	X		X									
Registration	X		X									
Investigational drug dispensing	X		X	X		X		X				
Retrieving leftover drugs			X	X		X		X		X		X
Checking of drug compliance			X	X		X		X		X		X
Physical examination	X		X	X		X		X		X	X	X
Blood pressure, pulse rate, and body temperature	X ⁹⁾		X	X		X		X		X	X	X
12-lead electrocardiography	X ⁹⁾		X							X	X	X
Laboratory tests ³⁾	X ⁹⁾		X	X		X		X		X	X	X
Pregnancy tests ⁴⁾	X											
Bladder diary records: Supplied	X			X		X		X				
Filled in												
Collected			X			X		X		X		X
Checked			X			X		X		X		X
Symptom score (IPSS, OABSS) evaluation	X		X			X		X		X		X
King's health questionnaire evaluation			X							X		X
Pressure Flow Study (PFS) ¹⁰⁾			X							X		X
Uroflowmetry			X ¹¹⁾			X ¹¹⁾		X ¹¹⁾		X ¹¹⁾		X ¹¹⁾
Post void residual measured by ultrasound	X ⁹⁾		X ¹¹⁾			X ¹¹⁾		X ¹¹⁾		X ¹¹⁾		X ¹¹⁾
Prostate gland volume measurement	X ⁹⁾											
Checking concomitant drugs/concomitant therapy ¹²⁾												X
Checking adverse events ¹²⁾												X

- 1) Obtaining informed consent: Obtained within the period of 28 days before registration in the observation period.
- 2) Assigning of patient identification codes: Assigned to patients providing informed consent.
- 3) Laboratory tests: Hematology tests, biochemistry tests, endocrinological tests and urinalysis will be performed. However, the urinalysis test urine sediment will only be performed at registration in the observation period and at registration in the treatment period.
- 4) Pregnancy tests: Required for female patients with childbearing potential. However, a pregnancy test will not be required for patients more than 1 year after menopause or patients in whom the possibility of pregnancy is medically ruled out. At tests before registration in the observation period, pregnancy tests (serum or urine) must be negative. The time window for performing the test is the period of 7 days before registration in the observation period.
- 5) Time window for registration in the treatment period: All observation and examination items at registration in the treatment period will be performed by registration in the treatment period, 2 to 4 weeks after registration in the observation period.
- 6) Time window for visits in the treatment period: Visits at weeks 2, 4, and 8 of the treatment periods will be allowed to be within the range of the standard date ± 3 days. The visit at week 12 will be allowed to be within the range of the standard date -3 days to the standard date $+7$ days.
- 7) Time window for the follow-up examination: This will be performed 1 to 2 weeks after the end of week 12 of the treatment period. If the patient discontinued during the treatment period, it will be performed 1 to 2 weeks after the final dose of the investigational drug.
- 8) At discontinuation: The designated observations and examination items will be performed as far as possible. For patients providing informed consent but not enrolled in the treatment period, the observations and tests relating to safety evaluation will be performed as far as possible.
- 9) If the designated observations or tests are performed in the period of 14 days before registration in the observation period, even if this is before informed consent is obtained, these can be used as data at registration in the observation period.
- 10) PFS will be performed on the same date as uroflowmetry and measurement of the post void residual by ultrasound as far as possible.
- 11) For evaluating BVE, measurement of the post void residual by ultrasound will be performed after uroflowmetry.
- 12) Concomitant drugs/concomitant therapy and evaluation of adverse events: These will be investigated from informed consent to the end of follow-up.

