3.1.1 Definition of Each Period for Each Patient

Each period described in this protocol is defined as follows.

Study period:	From the time of obtaining informed consent to the end of the follow-up examination
Observation period:	The period from registration in the observation period up to registration in the treatment period (registration in the treatment period will be performed between 2 to 4 weeks after registration in the observation period)
Treatment period:	From the time of registration in the treatment period to the end of week 12 of the treatment period
Follow-up period:	From the end of week 12 of the treatment period to the end of the follow-up examination (performed 1 week after the end of week 12 of the treatment period)

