5.1.10 Pregnancy Test

For patients of childbearing potential, serum or urine human chorionic gonadotrophin will be tested at the time point shown in [Table 5-2](#) to confirm that they are not pregnant. It is not necessary to perform the test in patients without childbearing potential.

Note) Women without childbearing potential are women who have undergone hysterectomy and postmenopausal women who have not experienced menstruation for at least 1 year with no associated medical reason such as administration of contraceptives

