7.1 Administration Procedure

7.1.1 Method of Administration

7.1.1.1 Observation period

In the observation period, placebo will be administered orally twice daily after breakfast and dinner for 2 to 4 weeks under single-blind conditions. The number of investigational drug capsules per dose is shown in [Table 7.1.1.1-1](#).

**Table 7.1.1.1-1 Number of Investigational Drug Capsules Per Dose
(Observation Period)**

Group	Number of capsules per dose
Placebo	Placebo × 2 capsules

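### Pregnancy is tested only before the placebo period and is not an exclusion at treatment registration; the numeric liver and renal limits are not carried over to the Week 0 results

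*Protocol*

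**What the plan says.** **Two registrations.** Each patient is registered first for the observation period and then for the treatment period. Protocol Section 7.1.1.1 covers the first: "In the observation period, placebo will be administered orally twice daily after breakfast and dinner for 2 to 4 weeks under single-blind conditions". TAC-302 is given only in the treatment period (7.1.1.2). Section 3.1.1 sets the gap: "registration in the treatment period will be performed between 2 to 4 weeks after registration in the observation period".

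**Pregnancy.** Exclusion 4.2.1(12), at observation registration, covers pregnant or breastfeeding women and any woman of childbearing potential "with a positive (urine or serum) pregnancy test result in the period of 7 days before registration in the observation period". The pregnancy row of Table 5-2 has a single mark, at Visit 1, and footnote 4 fixes the timing: "The time window for performing the test is the period of 7 days before registration in the observation period". Section 5.1.10 also refers to one occasion: "serum or urine human chorionic gonadotrophin will be tested at the time point shown in" Table 5-2. The nine exclusions of 4.2.2, at treatment registration, do not mention pregnancy.

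**Laboratory limits.** Exclusion 4.2.1(9) sets multiples of the upper limit of normal for AST, ALT, total bilirubin and creatinine. It opens: "Meeting the following conditions at laboratory tests performed in the period of 14 days before registration in the observation period". Table 5-2 schedules the laboratory panel again at Visit 2, and footnote 5 requires the Visit 2 examinations to be done by treatment registration. Section 4.2.2 gives no numeric limit for those results. It keeps a qualitative item (7) on clinically significant conditions, which includes severe liver and renal disease, and an open item (9): "Being determined to be ineligible for this study in the opinion of the principal investigator or subinvestigator". Section 5.1.9 has the investigator judge whether laboratory values are clinically significant changes.

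The synopsis criteria and Table 2 agree with the body on all of this.

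**The concern.** The pregnancy test and its short window are timed to the start of placebo, not to the start of the investigational drug. Most of the other medical exclusions (neurological disease, urinary disease, bladder and prostate cancer, cystocele, overflow incontinence, severe concurrent disease, catheter use) are stated again at treatment registration. Pregnancy is not. A woman who conceives during the observation period without recognising it would meet no listed exclusion and face no scheduled test before she could be assigned TAC-302.

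The laboratory issue is smaller and of a different kind. Fresh values exist at Week 0, but the limits that decided entry to the placebo period do not formally decide entry to the active period. Two sites could treat the same Week 0 value differently, and the protocol does not say whether that is intended.

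**Working it through.** The protocol gives no figure for the age of these tests at treatment registration, so there is nothing to reproduce first. The ages follow from its stated windows.

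**Inputs**
- Pregnancy test window: 0 to 7 days before observation registration (4.2.1(12); Table 5-2, footnote 4).
- Window for the values used in 4.2.1(9): 0 to 14 days before observation registration.
- Observation period: 2 to 4 weeks, that is 14 to 28 days (3.1.1).

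**Formula.** Age at treatment registration = days from test to observation registration + length of the observation period.

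| Item | Minimum | Maximum |
|---|---|---|
| Pregnancy test | 0 + 14 = 14 days | 7 + 28 = 35 days |
| Values judged against 4.2.1(9) | 0 + 14 = 14 days | 14 + 28 = 42 days |

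The second row is the age of the values to which the numeric limits apply. It is not the age of the newest laboratory data, because the panel is repeated at Visit 2.

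**Sensitivity of the 35 days.** Section 5 has a general sentence that lets tests from the 14 days before observation registration serve as registration data. If it governed the pregnancy test, the maximum would be 14 + 28 = 42 days. The pregnancy row does not carry footnote 9, which gives that allowance, and footnote 4 sets 7 days, so 35 is the better reading. Both ages run to treatment registration. The protocol gives no explicit interval from registration to first dose, and any delay would add to them.

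**The two exclusion lists side by side**

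| Item | Observation registration (4.2.1) | Treatment registration (4.2.2) |
|---|---|---|
| Pregnancy | Criterion (12), test within 7 days | No criterion, no scheduled test |
| AST, ALT, total bilirubin, creatinine | Criterion (9), numeric limits | Measured at Visit 2, no numeric limit |
| Severe liver or renal disease | Criterion (7) | Criterion (7) |
| Investigator judgement | Criterion (15) | Criterion (9) |

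Section 4.2 introduces both lists with wording about each registration, which might suggest that all items apply twice. Section 3.2.1 settles this: the patient is checked at the second registration against the criteria for the treatment period, which is the 4.2.2 list.

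**Number of patients.** The plan has 27 women. With 2:1 allocation and sex as a minimisation factor, about 27 × 2/3 = 18 would be assigned TAC-302. The test applies only to those of childbearing potential, and the documents do not say how many that is.

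**The case against.** **Other safeguards exist.** Refusing contraception is itself an exclusion (4.2.1(13)). Sections 7.2.1 and 12.5.1 require contraception, and 12.5.1 adds pregnancy reporting within 24 hours. Criterion 4.3(6) stops the investigational drug on pregnancy, and Section 3 uses that term for the observation-period placebo too, so a recognised pregnancy would end dosing before TAC-302. This stands and narrows the gap to unrecognised pregnancy despite contraception. It does not close the gap, since none of these measures detects a pregnancy.

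**The laboratory items are covered at Visit 2.** A reader might infer that TAC-302 starts on laboratory data up to 42 days old. The documents do not support that: the panel is repeated by treatment registration, the investigator must assess every value, and 4.2.2(7) reaches symptoms and findings, not only established diagnoses. What remains is the absence of a stated numeric limit for the Week 0 results.

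**The baseline.** A reader might also infer that an abnormal Week 0 value would hide a later drug effect. Section 12.1.5 judges observation-period events against observation registration and treatment-period events against treatment registration, so a rise on placebo is assessable in its own period. Laboratory tests then recur at Weeks 2, 4, 8 and 12 and at follow-up. Obscured drug effects are not shown.

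**A deliberate choice.** Synopsis and body agree, so this is not a slip in one table. The text of Sections 14.3.2.2 and 14.6, where reasons might be given, is not available in the public version. The sponsor may have had reasons that cannot be seen here.

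**Conclusion.** The pregnancy point holds. At registration for the first possible dose of TAC-302 the only scheduled test is 14 to 35 days old, and pregnancy is not among the exclusions then in force. The upper figure assumes that the 7-day window of footnote 4 governs.

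The group concerned is small. It would be wrong to count all 27 women as affected, because only those of childbearing potential are tested. After blind review the SAP splits women at 70 years for the primary-endpoint covariance analysis (7.3), which suggests, without proving, a largely postmenopausal group. Adding 12 weeks of treatment gives 35 + 84 = 119 days without a test up to the standard Week 12 date. That sum is correct, but most of it concerns monitoring on treatment, which is a separate question.

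The laboratory point holds only in its narrow form: Week 0 values are available but are not tied to the limits of 4.2.1(9). It does not follow that all 75 patients are exposed to a risk. The hepatic, renal or reproductive risk of TAC-302 cannot be judged from the public text. This is a cheap improvement in patient safety and in consistency between sites, and it does not affect the validity of the efficacy analysis.

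**What to change.** Reconcile 4.2.1, 4.2.2, the synopsis criteria and Tables 2 and 5-2 on two matters.

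1. Carry the protocol's existing pregnancy exclusion and test over to treatment registration, and mark the test at Visit 2 in both tables. The blood or urine already collected at Visit 2 can be used.
2. State whether the existing numeric limits of 4.2.1(9) apply to the Week 0 results or whether those results are left to 4.2.2(7), 4.2.2(9) and investigator assessment. Either answer should be explicit, so that sites act alike.

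No new threshold is proposed. The cost is protocol wording, one hCG test per woman of childbearing potential and possibly a few extra screen failures. If the limits are to apply, Week 0 results must also be in hand before registration; footnote 5 at present requires only that the examinations have been performed by then.
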